## **SPECIFIC AIMS**

Suicide is among the leading causes of death for adults with schizophrenia, with risk estimates being over eight times greater than for the general population. Epidemiological data indicate that 40-50% of adults diagnosed with schizophrenia experience suicidal thoughts, 20-50% of which make suicide attempts, and 4-13% die by suicide. While suicide research prioritizes depression and hopelessness, there is growing support for the role that symptoms of psychosis (e.g. hallucinations) play in risk. Further, this high suicide rate continues to be a major public health concern given the paucity of evidence-based interventions to reduce suicidality in this population. We propose to modify and evaluate the acceptability and preliminary effectiveness of Cognitive Behavioral Suicide Prevention for psychosis (CBSPp), a promising intervention requiring protocol and implementation modifications to increase its utility in community mental health (CMH).

**A long-term goal of our research program is to reduce premature suicidal death among adults with schizophrenia.** Our collaborative team developed and evaluated CBSPp, one of few suicide interventions tailored for adults experiencing psychosis. CBSPp integrates aspects of validated theories of suicide, including: Schematic Appraisal Model of Suicide, Cry of Pain, and Cognitive Theory of Suicide. Data show CBSPp improves global functioning and reduces depression, psychosis, suicidal ideation, and suicide attempt by targeting three cognitive components: information processing biases, appraisals, and schemas.

While CBSPp yields promising results, the following innovations will be pursued given feedback from clients and providers: 1) modify and shorten treatment; 2) develop a hybrid technology-assisted provider training; and, 3) develop a between-session treatment website with treatment reinforcing videos. Further innovations will be informed by interviews with CMH stakeholders for protocol and delivery modification input.

**Specific Aim 1: To modify CBSPp for clients with schizophrenia spectrum and other psychotic disorders (SSPD) receiving CMH services.** We will develop the provider training, client engagement enhancers, and conduct in-depth qualitative interviews to evaluate CBSPp materials and delivery protocol with stakeholders, including ≈15 adults with SSPD and suicidal ideation and/or attempt (SI/A) within 3 months of screening and ≈10 CMH staff, providers, directors and leaders. Qualitative data will be analyzed and subsequently presented to a panel of scholarly experts in suicide, psychosis, intervention, and implementation science for input. A systematic process will guide CBSPp modifications, refinement of the provider training and client engagement enhancers, and an open pilot trial will be conducted with 8 clients and 2 providers. Open pilot findings and explorations of organizational impact of implementation will be discussed with the expert panel, followed by any additional modifications from feedback and lessons learned.

**Specific Aim 2: To evaluate the feasibility and preliminary effectiveness of modified CBSPp in comparison to services-as-usual (SAU).** Adults with SSPD and SI/A within 3 months of screening (n=60) will be enrolled and randomized to CBSPp or SAU. A 4-wave design will include quantitative assessments at baseline (T1), mid-test (T2), post-test (T3), and follow-up (T4) with in-depth qualitative interviews at T4 for a random sample of adults in the CBSPp group (n=10). Providers (n=8) will be trained to deliver CBSPp and be assessed T1-T4 to evaluate the implementation process, including in-depth qualitative interviews at T4. We will monitor fidelity, acceptability, usability, and feasibility of the modified CBSPp.

**Aim 2a: To assess whether modified CBSPp is associated with reductions in SI/A (primary outcome), symptoms of psychosis, depression, and emergency/hospital service use over time.** Compared to SAU, the CBSPp group will experience significant reductions in SI/A

(H1), symptoms of psychosis (H2), symptoms of depression (H3), and emergency/hospital service use (H4).

**Aim 2b: To assess whether modified CBSPp is associated with clinical (hopelessness, defeat, and entrapment) and cognitive improvements (information processing biases, appraisals, and schemas) over time.** Compared to SAU, the CBSPp group will experience significant improvements in hopelessness (H5), defeat (H6), entrapment (H7), information processing biases (H8), appraisals (H9), and schemas (H10).

**Exploratory Aims: To develop hypotheses for future trials, we will explore mechanisms for reducing SI/A and improving clinical and cognitive mechanisms (mediators) involved in risk for SI/A or differential response to CBSPp (moderators). We will also collect and explore preliminary implementation data of implementation barriers and facilitators, acceptability, and scalability.**

**Impact:** This project is in response to RFA-MH-18-706, *Pilot Effectiveness Trials for Treatment, Preventative and Services Interventions*, and follows NIMH's strategic plan to develop ways to tailor existing and new interventions to optimize outcomes (3.2) and test interventions for effectiveness in community practice (3.3). Successful completion of this proposal will result in a novel intervention that improves cognitive processes related to suicide risk, psychosis and depression, and reduces SI/A. Our future research will build on this work to evaluate large-scale CBSPp effectiveness and implementation within multiple sites of CMH.

## BACKGROUND

### **Suicide among Adults with Schizophrenia**

Suicide is among the leading causes of death for adults with schizophrenia with risk estimates over eight-fold greater as compared to the general population. Moreover, 40-50% of adults with schizophrenia have suicidal thoughts, of which 20-50% make suicide attempts, and 4-13% end their life by suicide. The high suicide rates among adults diagnosed with schizophrenia have received much attention, yet, evidence-based treatments are highly limited and suicide continues to be a major public health problem.

### **Risk Factors for Suicide in Schizophrenia**

The relationship between schizophrenia and suicide is quite complex as researchers continue to examine what makes an individual with schizophrenia at risk for ending his or her life. A history of suicidal behaviors (ideation and/or attempt) is the strongest predictor of future behaviors. Additional risk factors for suicide include race/ethnicity, gender, education, and poverty. More specifically, risk is increased when an individual is single, male, white, socially isolated, unemployed, impulsive, has a history of depression, a family history of suicide, greater insight, treatment noncompliance, severe symptoms, and recent loss.

Among adults with schizophrenia, 22%-75% experience depressive symptoms including low mood and hopelessness, which are empirically demonstrated factors that increase risk for suicide. While research has largely focused on depression and hopelessness, there is growing support for the role that positive symptoms of psychosis play in suicide risk with data showing delusions and auditory hallucinations increase suicidal behavior. Positive symptoms are furthermore shown to weaken social skills, increase avoidance of social contact, and impair development and maintenance of supports, which are known to be important protective factors in suicide risk. The importance of risk and protective factors notwithstanding, it is critical to examine and understand mechanisms involved in suicidal ideation and attempt.

## **Mechanisms of Suicidal Ideation and Attempt**

Williams' Cry of Pain (CoP) theory of suicide is grounded within ecological explanations of stress and defeat with the belief that feelings of extreme and uncontrollable stress are important and necessary components contributing to mechanisms of suicide. Components of CoP include: the presence of stressors, perception of stressors, cognitive biases, hopelessness, feelings of no rescue from others, and means for suicide. Beyond defeat, entrapment, and hopelessness in CoP, the Schematic Appraisals Model of Suicide (SAMS) suggests positive self-appraisals provide a key source of resilience by buffering suicidal thoughts and behaviors.

As a modified version of CoP, the SAMS is one of few theoretical models of suicide risk that specifically considers symptoms of psychosis. It builds on components of CoP to provide a theoretical framework in which psychological mechanisms of suicidal thoughts and behaviors are better understood. The SAMS specifies the following 3 mechanisms shown empirically to relate with suicidal thoughts and behaviors: information processing biases (biases in attention, memory, reasoning, and problem solving), appraisals (appraisals of the current situation, past, future, and self), and schemas (patterns of thoughts/behaviors which categorize information about the self, others, and world). Nodes representing suicidal thoughts associate with representations of sensations, cognitions, and emotions, including a link between suicide and forms of escape.

## **RESEARCH DESIGN FOR AIM 1 OPEN PILOT (not including stakeholder phase or RCT)**

### **Study Site**

The study will take place at Washtenaw County Community Mental Health (WCCMH). WCCMH provides mental health services to adults with severe mental illness and developmental disability. They are the primary CMH provider in Washtenaw County, and represent a public mental health system encompassing the diversity of Michigan (race, ethnicity, socioeconomic status, organizational services, insurance/payment types). WCCMH offers a breadth of programs including crisis residential services, case management, outpatient mental health, medication management, assertive community treatment, and more.

### **Study Participants and Procedures**

**Client participants.** Includes adults 18 to 65 years of age clients who have attended/engaged with any services offered at WCCMH within 6 months of contact, English-speaking, have at least a 6th grade reading level measured by the Wide Range Achievement Test 4 (WRAT-4), Schizophrenia spectrum or other psychotic disorder (SSPD) based upon The Mini International Neuropsychiatric Interview (MINI), and Suicidal ideation or attempt (SI/A) within 3 months of assessment based upon the Columbia-Suicide Severity Rating Scale (C-SSRS). Exclusions involve the following: requiring emergency care (e.g. imminent plan to harm self) as determined by trained research staff administering the Columbia-Suicide Severity Rating Scale (C-SSRS), or determined to not be appropriate for behavioral treatment according to own judgment in consultation with a treating clinician at the research site (WCCMH). Clients also must have the capacity (cognitive capacity) to participate and both case managers and providers delivering treatment will evaluate this. We expect the following time to complete study activities:

- Clients in open trial of Aim 1: We expect the amount of time to be 20.5 hours total: 30 minute screener, weekly one-on-one therapy sessions with a trained provider for up to 10 weeks (10 hours maximum), use of treatment website with treatment reinforcing videos between treatment sessions during the 10 weeks of treatment (5 hours approximately), 1-hour surveys at 4 time-points (4 hours total), and an interview at the end of study (1 hour).

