## **Recruitment, Screening, and Enrollment**

**Client participants.** Designated WCCMH personnel will identify client participants who meet criteria for study inclusion based upon DSM SSPD diagnosis and endorsement of suicide ideation and/or attempt within 3 months per documentation of the C-SSRS. Case managers will be notified if their client(s) meet criteria and will be prepared with instructions by the research team (see scripts) on how to present the study given clients' potential eligibility. Clients who are interested to learn more will be instructed to either: 1) reach out to research staff (RS) via phone, or, 2) give consent for the case manager to give the potential participant's contact information to RS so they can be contacted via phone and learn of next steps (eligibility, consent, enrollment, assessment). RS will schedule an in-person meeting with clients who are interested in learning more about the at WCCMH (coordinating with an already scheduled appointment with a provider). In this meeting, RS will describe the study (see scripts) and review the informed consent form. If consent is obtained, the screening tool will be administered to determine eligibility for enrollment (approximately 15 minutes long). Screening will involve use of The Mini International Neuropsychiatric Interview (MINI) to confirm a SSPD based upon criteria of the DSM-5. A 3-month history of SI/A will be confirmed using the C-SSRS. Lastly, the Wide Range Achievement Test 4 (WRAT-4) will be administered to confirm at least a 6th grade reading level in English given use of CBSPp materials.

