## **Procedures After Enrollment**

**Client participants in open trial of Aim 1.** Clients participating in the open trial of Aim 1 will:

1. Complete a 1-hour survey following enrollment (not a separate visit), including questions about personal characteristics, symptoms of psychosis, depression, suicide thoughts and suicide attempt.
2. Attend weekly one-on-one therapy sessions with a trained provider for up to 10 weeks. Our research staff will set this and therapy sessions will take place at Washtenaw County Community Mental health at your convenience. Therapy sessions will be focused on improving thoughts of suicide and preventing suicide attempt. All therapy sessions will be audio recorded so we can check that therapists are correctly giving this treatment.
3. Complete a 1-hour survey approximately in 1-month, 3-months, and 5-months. Surveys will be focused on experiences with symptoms of psychosis, depression, suicide thoughts and suicide attempt.
4. Use a treatment website that we will provide between therapy sessions with short videos to help you practice skills you will learn in treatment.
5. Attend a 1-hour interview with research staff at the end of the study which will be audio recorded and include questions about experiences in the study.

If client participants refuse to participate after determined to be eligible, enrolling in the study, being assigned to a provider, and/or starting study activities (surveys and/or treatment), they will be removed from the study and thanked for their time.

If a client participant leaves WCCMH services (e.g., moves, ends services, switches to different service provider) during the study, their participation in the study will end.

Client participant attendance will be tracked as one of our goals is to learn more about acceptability and feasibility of the intervention. While 10 sessions are what providers will be trained to deliver, clients may choose not to attend all sessions. It is important to note that

there will be no consequences for not attending sessions; participants can remain as active as they choose to be with treatment and survey completion.

If a provider leaves during the study and/or during the process of delivering CBSPp with a client participant, we will re-assign the client(s) to a different therapist who has been trained in CBSPp. If needed, we train additional providers in preparation for resuming treatment with client participants whose previous provider left.

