## Assessment

**Aim 1 Open pilot trial Quantitative data.** Clients will complete comprehensive assessments at baseline (T1), mid-test (midpoint of total CBSPP sessions; T2), post-test (endpoint of CBSPP sessions; T3), and follow-up (3 months after CBSPP session endpoint; T4). Measurement shown below in Table 3.

Construct	Instrument(s)	Time	Reporter
Aim 2a: To assess whether modified CBSPP is associated with reductions in SI/A (primary outcome), symptoms of psychosis, depression, and service use over time.			
SI/A	Columbia Suicide Severity Rating Scale (CSSRS) 	T1,T2,T3,T4	CT, RS score
Psychosis	Positive and Negative Syndrome Scale (PANSS) 	T1,T2,T3,T4	CT, RS score
Depression	Calgary Depression Rating Scale (CDRS) 	T1,T2,T3,T4	CT, RS score
Aim 2b: To assess whether modified CBSPP is associated with clinical and cognitive improvements over time.			
Clinical	Hopelessness	Beck Hopelessness Scale (BHS) 	T1,T2,T3,T4
	Defeat	Defeat Scale 	T1,T2,T3,T4
	Entrapment	Entrapment Scale 	T1,T2,T3,T4
	Social support	Quality of Life 	T1,T2,T3,T4
	Coping	Coping in Stressful Situations Inventory (CSSI) 	T1,T2,T3,T4
Cognitive	Information processing biases	Modified Stroop task 	T1,T2,T3,T4
	Appraisals	Resilience Appraisals Scale (RAS)  Reappraisal Subscale of Emotion Regulation Questionnaire (ERQ) 	T1,T2,T3,T4
	Schemas	Suicide Concept Sort Task (SCT) 	T1,T2,T3,T4
			CT
Key: T1 = baseline; T2= mid-test; T3= post-test; O= ongoing; CT= clients; RS score = research staff score ratings as this is a clinical interview and not a self-report measure.			

**Aim 1 Open Pilot trial Qualitative assessment.** We will systematically evaluate the modified CBSPP using in-depth face-to-face qualitative interviews with all clients in the open pilot trial. Topics will focus on: 1) perceptions about their experience receiving the treatment, feedback regarding treatment impact and observed mental health outcomes, experiences with the added engagement enhancers, and factors impacting possible sustainability of maintaining the treatment at community mental health over time.

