## Statistical Design and Analysis

**Aim 1 open pilot quantitative data analysis.** A focus of Aim 1's open pilot is to implement the CBSPP treatment and assessments in preparation for potential modifications prior to Aim 2. We will preliminarily explore outcomes (SI/A, symptoms of psychosis, depression, emergency/hospital service use, hopelessness, defeat, entrapment, information processing biases, appraisals, and schemas) in preparation for Aim 2. Given the open pilot is small in size (n=8 clients), we don't have power to detect changes over time in Aim 1. Therefore, quantitative data will be examined at the univariate and bivariate level for distributions and associations between variables. Measures of dispersion (mean, standard deviation, variance, range) and distribution (kurtosis, skewness) will be computed. Scatterplots will be generated to examine linearity and outliers for bivariate relationships using Chi-Square analysis (categorical variables), analysis of variance (ANOVA; scaled variables), and paired samples t-tests (continuous variables) in SPSS28.

**Aim 1 open pilot qualitative data analysis.** Qualitative in-depth interviews data were transcribed and coded using Dedoose. Transcripts were independently coded by two research assistants (RAs) in preparation for codebook development using an open coding technique to generate themes across qualitative questions (Saldana, 2016). Grounded theory methods were utilized for analysis (Charmaz, 2014). The PI met with both RAs to discuss emerging themes after a first round of coding and agreed upon a final codebook. Both RAs completed a second round of coding using the final codebook and the PI resolved any disagreements to achieve inter-coder consistency. Themes were ultimately organized into a final framework and the following strategies for rigor (Padgett, 2016) were included in the study: 1) triangulation, specifically analytic triangulation (more than one coder), 2) audit trail, and 3) member checking with stakeholder participants (i.e., in provider, peer, and client meetings).

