## **Risk Management**

Risk status will be formally determined and recorded at the T1-T4 quantitative assessments. There will not be an assessment of suicide risk conducted by research staff during the treatment sessions for participants receiving CBSPp or SAU, as licensed clinicians conduct a comprehensive risk assessment as part of standard clinical protocol.

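### Does using the C-SSRS both to select clients and to measure SI/A, with no stated look-back, build a false improvement into the open pilot?

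*Combined protocol and SAP*

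**What the plan says.** Under Study Participants and Procedures, the entry criterion is "Suicidal ideation or attempt (SI/A) within 3 months of assessment based upon the Columbia-Suicide Severity Rating Scale (C-SSRS". Recruitment, Screening, and Enrollment adds that "A 3-month history of SI/A will be confirmed using the C-SSRS". The eligibility paragraph also excludes anyone whom research staff, using the same scale, judge to need emergency care.

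Procedures After Enrollment places the baseline survey at the enrolment contact: "Complete a 1-hour survey following enrollment (not a separate visit". For the later waves it says "Complete a 1-hour survey approximately in 1-month, 3-months, and 5-months". The Assessment section ties T2 and T3 to the midpoint and end of the sessions, and T4 to "follow-up (3 months after CBSPP session endpoint; T4".

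The SI/A row of the measurement table names only the "Columbia Suicide Severity Rating Scale (CSSRS", at T1 to T4. Neither that section nor Statistical Design and Analysis gives a recall period, an item set or a score. The analysis section says that 8 clients give no power to detect change, and for that reason limits the quantitative work to univariate and bivariate exploration. Among its tools it lists "paired samples t-tests (continuous variables) in SPSS28".

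Risk Management states that "Risk status will be formally determined and recorded at the T1-T4 quantitative assessments". The definition of High Risk that follows uses the past week for ideation and the time since the previous assessment for attempts. Those windows serve safety classification.

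**The concern.** Every client is positive for SI/A over the 3 months before entry, and T1 is taken at that same contact. If T1 were scored over 3 months, the result would be 100% by construction and could only stay level or fall. If later waves were scored over the time since the previous visit, the window would also shorten after T1 and vary between waves. The pilot has no comparator, so a fall from selection and window length would look the same as a response to therapy.

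The pilot explores SI/A ahead of Aim 2, and under Specific Aim 1 its findings go to an expert panel before any further modifications. The fear is that the panel would take an artefact as an early sign that CBSPp works or, if the T4 window is longer, as relapse.

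**Working it through.** The plan gives no event rate, SD or effect size for the pilot, so there is no stated figure to reproduce. The checks below assume no therapy effect. Their rates are assumptions and are shown as a range.

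**1. Wave timing.** Procedures After Enrollment puts T2 to T4 at about 1, 3 and 5 months. For the Assessment section, take 10 weekly sessions and a month of 13/3 = 4.33 weeks:
- T2: 5/4.33 = 1.2 months
- T3: 10/4.33 = 2.3 months
- T4: (10 + 13)/4.33 = 5.3 months

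The two descriptions roughly agree.

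**2. Yes/no score.** Let q be the monthly chance of any SI/A (0.3, 0.5, 0.7), with independent weeks.
- Chance of any SI/A in w weeks: P(w) = 1 − (1 − q)^(w/4.33)
- Chance of meeting the entry rule: S = P(13) = 65.7%, 87.5%, 97.3%
- For a look-back w lying inside the entry window, the T1 figure among those selected is P(w)/S. At a later wave with no overlap it is P(w).

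| Scoring | T1 (%) | Later (%) | Fall (points) |
|---|---|---|---|
| Last week at every wave | 12.0 / 16.9 / 24.9 | 7.9 / 14.8 / 24.3 | 4.1 / 2.1 / 0.7 |
| Past month at every wave | 45.7 / 57.1 / 71.9 | 30 / 50 / 70 | 15.7 / 7.1 / 1.9 |
| 3 months at every wave (T4) | 100 | 65.7 / 87.5 / 97.3 | 34.3 / 12.5 / 2.7 |
| 3 months at T1, then since last visit (T2 at 1 month) | 100 | 30 / 50 / 70 | 70 / 50 / 30 |
| Same (T2 at 5 weeks) | 100 | 33.7 / 55.1 / 75.1 | 66.3 / 44.9 / 24.9 |

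Falls are taken from unrounded values. One client in 8 is 12.5 points. The past-month fall is 8 × 0.157 = 1.3 clients at most, and the last-week fall is 8 × 0.041 = 0.3 of a client at most.

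Letting clients differ in their rates (Beta, a + b = 2, same means) gives past-month falls of 57.3 − 46.4 = 10.9, 66.7 − 60.0 = 6.7 and 78.1 − 74.9 = 3.2 points. The last-week falls are 18.6 − 15.8 = 2.8, 25.0 − 23.2 = 1.8 and 35.9 − 35.0 = 0.9 points.

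**3. Apparent relapse at T4.** With since-last scoring and the Assessment timing (5 weeks before T3, 13 weeks before T4), the figures go from 33.7 / 55.1 / 75.1% to 65.7 / 87.5 / 97.3%, a rise of 22 to 32 points. With the 1, 3 and 5 month timing, both gaps are 2 months, both waves give 51 / 75 / 91%, and the rise vanishes.

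**4. Severity score with a paired t-test, n=8, two-sided 0.05.** Weekly 0 to 5 severity was simulated as a stable trait plus an autocorrelated state (trait share 0.3 or 0.7, weekly correlation 0.8, weekly prevalence 0.2 or 0.4). Clients were selected on any positive week in 13. The nominal rate of a significant fall is 2.5%.
- Past week, T1 to T3: significant fall in 2.5 to 3.6% of pilots.
- Worst point over 3 months, T1 to T3: 6 to 14%.
- 3 months at T1, then since last visit, T1 to T2: 43 to 54%.

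Removing clients with a current score of 5, as a stand-in for the emergency-care exclusion, makes the past-week mean go from 0.90 to 0.88 or 0.66 to 0.60 at prevalence 0.2. At prevalence 0.4 it goes from 1.15 to 1.18 or 0.94 to 0.98. Trimming the top at entry works against a fall and can turn it into a slight rise.

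**5. What the plan prescribes.** The large figures need two windows from elsewhere: the eligibility window carried into the T1 outcome, and the High Risk window for attempts extended to all SI/A. For ideation the High Risk definition uses the past week, which is the scoring with the smallest artefact.

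**The case for a change.** The best argument for a change is that low power does not protect against bias. Under the mixed scoring, 8 of 8 positive at T1 would become about 2 to 6 of 8 at T2 (8 × 30% = 2.4 to 8 × 75.1% = 6.0), which is visible without any test. The paired t-test is still on the list, there is no control arm, the panel will see the findings, and a sentence on scoring would cost little.

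Part of this stands. The outcome definition is not written down, and an analyst who mixed windows would produce a misleading fall. The rest is weaker. The harm needs an unusual scoring choice and then a causal reading of 8 clients, against the plan's own statement on power. Fixing the look-back would not make the change attributable to CBSPp, because selection remains and standard care continues alongside the therapy. Nor is a new look-back sure to be usable: the qualitative analysis section speaks in the past tense of interviews that come at the end of study participation, so the C-SSRS data were probably already collected.

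**Conclusion.** The concern is right on the facts: same scale for entry and outcome, T1 at the entry contact, no stated look-back. It does not call for a change. With a common short window the spurious fall is about 0.7 to 4 points (last week) or 2 to 16 points (past month), and the emergency-care exclusion may cancel or reverse the last-week figure. The 25 to 70 point fall belongs to a scoring that the plan does not set out.

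These sizes rest on an assumed monthly chance of 0.3 to 0.7, independent weeks and no therapy effect. They show direction and range and are not estimates for this trial.

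Little hangs on the result. The pilot is declared underpowered and exploratory, the Aim 2 sample of 60 is already set, and the randomised comparison with services-as-usual is not biased by how the pilot is scored. A competent analyst would score all waves over the same period, list attempts with the time covered, and describe pre-post change without attributing it to therapy. The gap is one of missing detail.
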